**Step 9: For all participants who decide to take PrEP, the study nurse will draw blood to test for baseline creatinine tests**

- Women with low creatinine can participate in the study but can only receive PrEP if their eGFR >60mL/min
- Test results will be received in 24-48 hours. If eGFR <60mL/min then the nurses will call participant to return and immediately stop using PrEP until they have a normal creatinine result (can return in following month)

**Step 10:** Participants who opt to take PrEP will receive counselling on the risks and benefits of PrEP. Following the counseling they will be asked: “Do you want to start taking PrEP today to prevent HIV? You will need to take it daily for it to be effective.” Her response will be recorded.

If yes:

1. The nurse will provide the participant with a 1-month supply of TDF-FTC and invite her to return in 1 month for her next study visit (after then they will receive 3 months prescriptions to correspond with their quarterly PrEP-PP study visit).
2. Nurses will provide contact information to the participant and ask her to call to report any side effects or adverse events while on PrEP, and nurse will track and report serious adverse events to study PIs, Pediatrician, and Obstetrician to decide on how to treat women and infants who have adverse events.

If she says she does not want to start PrEP, woman will be in the deferred PrEP arm:

1. The nurse will schedule her to return in 3 months for the follow-up study visit

**Step 10:** Participants will receive study staff contact information, instructions to call with any questions, and will be scheduled for their next visit in 1 month if on PrEP, or 3 months if not on PrEP, for the next study visit

**Step 11:** The study counselor will provide the mother with an appointment card and invitation for her partner to return to receive couples' HIV testing and counseling (if in a relationship). The session will end by encouraging the client to implement her/his risk-reduction plan (including PrEP if applicable and consistent condom use, couples testing) to prevent HIV acquisition.

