**Step 4:** *For participants on PrEP*, the study nurse performs a blood draw for creatinine clearance and a finger prick for DBS testing for adherence measures and (if applicable for this visit). See Table 1 for study calendar.

**Step 5 (for women on PrEP):** At each visit the study counselor will ask, and record responses, all participants on PrEP about any side effects associated with TDF/FTC, including diarrhea, nausea, fatigue, headache and rash (which are seen in about 10% of participants during the initiation of therapy). We will encourage participants to contact the study nurse if they experience side effects between visits.

**PrEP retention methods to improve adherence:** Each study visit will include counselling from peer counsellors who will discuss the importance of retention and adherence to PrEP for effectiveness. We will adapt messages from ongoing PrEP studies conducted by co-I [name] and team. We will also provide participants with a brochure to take home that discusses retention, adherence and side effects of PrEP. Each visit will include group and individual counselling. Group counselling will be led by a mother who has successfully taken PrEP for 3+ months to guide a discussion about the importance of retention, reminders on how to take the medication daily and how to address side-effects (e.g. nausea, headaches, etc).

**Step 6:** PrEP provision (for 1 or 2 months) and appointment reminder

*Follow-up & retention:* Tracing information will be taken at the enrolment visit and updated at each study visit. Retention activities will focus on scheduled measurement visits. Following our established approach in this

setting, we will provide reminder calls to participants before their measurement visits, and initiate tracing, including home visits, for women who do not attend the measurement visit within one week of the scheduled visit.

*PrEP provision:* monthly for the first 3 months, and then 2-months intervals after that. Participants on PrEP will have regular monitoring with laboratory tests, including creatinine levels to check for changes in renal function and dried blood spots (DBS) for adherence measures. Those with HBsAg+ will be excluded from the study. We will test for HIV seroconversion at every study visit.

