#### *Survey measures*

At study measurement visits, questionnaires will be administered to mothers participating in the study. Following standard procedures, the questionnaires will be translated into isiXhosa and Afrikaans and back translated to ensure appropriate phrasing. Questionnaires will include:

- Basic demographic information and obstetric history (enrollment only)
- Partner's HIV status
- Sexual behaviors in the past month and week including # of sex partners, type of sex, and frequency of sex and condom use
- Substance use information using the AUDIT-C and DAUDIT scales
- Risk perception scales
- Partner, community and social support for PrEP
- For PrEP users, questions related to PrEP adherence according to self-report (the 3-day and 1-month recall and a visual analog scale) and pharmacy-based pill counts will be conducted at each study measurement visit.

- Additional schedules will be used to collect data on symptoms in mothers that are potential side-effects of PrEP use (at all study visits)
- We will also use short questionnaires to collect data on all women's experiences in the study, and the acceptability of the PrEP initiation, including what kind of services were offered at each visit (e.g. counseling, peer mentorship, and IEC materials, medication)
- Self-reported symptoms related to STIs
- This will focus on the positive and negative aspects of their experiences of PrEP initiation in pregnancy and breastfeeding and any factors associated with PrEP initiation, retention, and adherence.

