Health outcomes and adverse events	Any side-effects, change in creatinine clearance, any negative maternal or neonatal outcomes (for mother and infant) compared by PrEP use/non-use	Electronic provider log (REDCap)	Weekly and quarterly
Infant growth outcomes	Measure infant weight, length, z-score and any adverse events in infants compared by PrEP use/non-use	Electronic provider log (REDCap)	Weekly and quarterly

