***Methods/Approach:***

Tabulation of adverse effects with each treatment group:

- (1) Number of events by type of event
  - Describe the frequency of any laboratory or self-reported side effects (e.g. changes in creatinine clearance, or self-reported side-effects [GI symptoms, headache, and etc]). Analyses will include pure-count and person-time approaches. Confidence intervals will be calculated following the method of Breslow and Day. We will also describe pregnancy (miscarriage, stillbirth) and infant outcomes over time (including birthweight, gestational age at delivery, pregnancy loss) by PrEP status (on/off PrEP and by persistence to PrEP)
- (2) Number of subjects by highest grade of event
- (3) Reasons for termination of treatment

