#### Adverse events and serious adverse events (PrEP use defined as taking PrEP in last 30 days)

	PrEP users (N)	%	PrEP non-users (N)	%	Comment
Adverse event reported (n=# of events and # of participants)					
Type of events					
Serious adverse event reported (n= # of events)		% over # of participants in study			
Type of events					
HIV testing					

HIV ab+					
HIV ag+					
HIV ag/ab+					

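### The visit procedure and SAP direct side-effect questions to PrEP users, yet SAP Table 1 compares side effects by PrEP use; conflicting passages leave that comparison open to unequal ascertainment

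*Combined protocol and SAP*

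**What the plan says.** **Who is asked.** In protocol section 5, the heading of Step 5 of the follow-up visit restricts it to PrEP users, and its text reads: "At each visit the study counselor will ask, and record responses, all participants on PrEP about any side effects associated with TDF/FTC". The named symptoms are diarrhoea, nausea, fatigue, headache and rash. There is no parallel step for women not on PrEP. At enrolment, only the branch for women who accept PrEP tells the nurse to "ask her to call to report any side effects or adverse events while on PrEP".

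**When they are seen.** The enrolment steps say that women "will be scheduled for their next visit in 1 month if on PrEP, or 3 months if not on PrEP". The PrEP provision paragraph adds refill contacts "monthly for the first 3 months, and then 2-months intervals after that".

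**What the SAP does with the data.** SAP Table 1 (study measures for Aim 1) lists as a secondary outcome "Any side-effects, change in creatinine clearance, any negative maternal or neonatal outcomes (for mother and infant) compared by PrEP use/non-use". SAP section 2.6 calls for "Tabulation of adverse effects with each treatment group". The adverse-event template in SAP section 4 has user and non-user columns, with "PrEP use defined as taking PrEP in last 30 days".

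**What points the other way.** The protocol's Survey measures list includes: "Additional schedules will be used to collect data on symptoms in mothers that are potential side-effects of PrEP use (at all study visits". That item is not limited to PrEP users, although the item just before it is. The Adverse events paragraph has mothers in general asked about intercurrent medical events. The opening of section 5 has all enrolled women returning every 3 months. The introduction to the follow-up visits gives a 1-month visit without reference to PrEP status.

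**The concern.** A comparison of symptom frequency is interpretable only if symptoms are sought in the same way in both groups. Read together, Step 5, the call-in instruction and the 1-month versus 3-month return give users a named checklist, an extra reporting channel and an earlier enquiry. If that is how the study ran, users could show more side effects with no drug effect at all.

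This is distinct from confounding by the choice to take PrEP, and would arise even under randomisation. Covariate adjustment does not remove it, because the difference lies in how the outcome is measured. The person-time analysis in SAP section 2.6 does not remove it either: it corrects for length of follow-up, not for how often or how directly a woman is asked. No passage in the SAP addresses unequal ascertainment.

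At stake is the tolerability message. The study is meant to inform policymakers, and the SAP allows its report templates to be split by PrEP status for the DSMB.

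**Working it through.** The documents give no sample size, power or error rate for this comparison, so there is no figure to reproduce. The check has two parts.

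**1. Passages side by side**

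| Question | Asymmetric by PrEP status | Not split by PrEP status |
|---|---|---|
| Who is asked about symptoms | Protocol Step 5; SAP 2.5 takes side effects from CRFs of women who take PrEP; SAP Part 3 template records symptoms while on PrEP | Survey measures symptom schedule; maternal adverse-event enquiry |
| First return | Enrolment steps: 1 month on PrEP, 3 months otherwise | Opening of section 5 (every 3 months); introduction to follow-up visits (1 month) |
| Later contacts | Refill contacts for users | Protocol Table 1 survey row, which (as extracted) is marked wherever the refill row is, and in two more columns |

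SAP 2.5 states that individual and disease factors come from all participants, but places side effects with PrEP takers. That leans towards users only without settling it.

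**2. Size under no drug effect**

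Let p be the chance of reporting a symptom at one enquiry. The documents give no background rate. Their only figure is about 10% for side effects at PrEP initiation, so p is an assumption, taken here from 10% to 40%. With k independent enquiries, the cumulative chance of any report is 1 − (1 − p)^k.

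*Two enquiries for users (months 1 and 3), one for non-users (month 3).* The ratio is [1 − (1 − p)²]/p = 2 − p.

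| p | Users | Non-users | Ratio |
|---|---|---|---|
| 10% | 19.0% | 10% | 1.90 |
| 20% | 36.0% | 20% | 1.80 |
| 30% | 51.0% | 30% | 1.70 |
| 40% | 64.0% | 40% | 1.60 |

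*Whole follow-up.* The SAP continuation and persistence template lists returns at 1, 3, 6, 9, 12, 15 and 18 months. Assume users are asked at all 7 and non-users at the last 6.

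| p | Users, 1 − (1 − p)^7 | Non-users, 1 − (1 − p)^6 | Ratio |
|---|---|---|---|
| 10% | 52.2% | 46.9% | 1.11 |
| 20% | 79.0% | 73.8% | 1.07 |
| 30% | 91.8% | 88.2% | 1.04 |
| 40% | 97.2% | 95.3% | 1.02 |

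*Fully persistent symptoms.* If a woman either has the symptom throughout or never has it, one enquiry finds it as surely as seven, and the ratio is 1.0.

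*Same questions at the same visits.* The ratio is 1.0.

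*Step 5 followed literally.* Non-users have no solicited symptoms, so the comparison has no comparator.

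**The case against.** The strongest reply is that non-users probably are asked. The symptom item in Survey measures refers to mothers at all study visits and, unlike its neighbour, is not limited to PrEP users. A survey is given at each visit, and mothers in general are asked about medical events. The analysis is also largely descriptive: no test of side effects is specified, and the SAP Part 3 side-effect template has no non-user column.

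Much of this stands, and it rules out three stronger readings.

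- A reader might infer that symptoms are solicited from users only. The Survey measures item prevents that conclusion. The supportable statement is that the visit procedure and the SAP direct solicitation to users while another passage may extend it to everyone.
- A reader might infer that ordinary symptoms will appear as drug effects. They may. The result depends on which passage was followed.
- A reader might count monthly refills as enquiries and take three against one by month 3, giving ratios of 1.96 to 2.71 over p = 40% to 10%. No passage says symptoms are asked at a month-2 refill, and the SAP templates show a single refill visit before visit 2.

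The month-3 ratios are also fragile. The SAP defines no month-3 cumulative symptom endpoint. Enquiries on the same woman are not independent, and a non-user asked at month 3 could recall the whole interval. The adverse-event template's 30-day definition of use also lets a woman change group over time.

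What the reply does not do is secure equal ascertainment. The general question on medical events is not a named symptom checklist. Even on the generous reading of Survey measures, the enrolment steps still give users an earlier enquiry and an instruction to call.

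**Conclusion.** The concern holds as an unresolved conflict that leaves a stated secondary comparison open to differential ascertainment. It is not a demonstrated bias of known size. Under no drug effect the spurious ratio could be:

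- 1.0, if both groups are asked the same questions at the same visits, or if symptoms are fully persistent;
- about 1.02–1.07 for cumulative reporting over the SAP template visits, at 20–40% per enquiry (1.11 at 10%);
- about 1.6–1.9 for two enquiries against one by month 3, at 10–40% per enquiry;
- undefined, for want of a comparator, if Step 5 is applied as written.

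The ratios above 1.0 rest on assumed reporting rates, independent enquiries, an equal chance of reporting at each enquiry and fixed exposure groups. The existence of the conflict rests on none of these. The initiation, continuation and persistence outcomes are not affected by this point.

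**What to change.** 1. Reconcile follow-up Step 5 with the Survey measures symptom item, and the enrolment return times and PrEP provision paragraph with the other visit schedules in section 5 and protocol Table 1.
2. Give the Survey measures symptom schedule to all participants at each shared study visit, in the same neutral wording and without asking for attribution to PrEP.
3. In SAP Table 1, SAP section 2.6 and the adverse-event template, limit the use/non-use comparison of symptoms and non-serious adverse events to those shared visits, with one recall window covering the time since the previous shared visit.
4. Report symptoms from the 1-month visit, refill contacts and telephone calls in users only, as a descriptive table with no comparator.
5. If non-users were in fact not asked, drop the side-effect comparison and report users only.

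The cost is a few minutes of questions for non-users, who already complete a survey at each visit, and a few sentences in the SAP. If data collection is finished, items 3 to 5 can still be applied. There is one real drawback. The protocol's background section says early side effects dissipate over a few weeks, so a comparison at shared visits may under-capture them; the users-only table would still show them. These changes equalise ascertainment only; confounding by the choice to take PrEP remains.

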#### **Laboratory tests in women on PrEP:**

- **Renal function (in all women on PrEP):** Blood draws for creatinine levels will be taken at baseline, 3-month follow-up and at the end of the study, as per SA HIV Clinician Guidelines [26].
  - At enrollment: women with eGFR<60ml/min will be excluded from the study
  - At 3-month follow up: Women will not be able to continue taking PrEP with an eGFR <60m/min but will be able to continue to participate in the study. If their creatinine results change at the following visit they will be eligible to start PrEP.
- **DBS:** Dried blood spots will be prepared from finger pricks every three months in women on PrEP to evaluate adherence.
  - DBS cards will be prepared and stored following standard protocols and stored at -80°C for analysis at the end of the study with the clinical pharmacoanalytic laboratory of [name] at UCT. Using techniques developed by [name] at University of Colorado [16] adherence will be defined as red blood cells containing TDF-DP  $\geq 40\text{ng/dl}$  which is indicative of daily dosing [16]. As supplementary measures of PrEP adherence, we will use self-reported items that we will adapt from previous studies (including visual analogue scales as well as 3-day, 30-day and last visit recall questionnaires) (22-25), and pharmacy refill records to compare objective versus subjective measures and report on the effectiveness of each measure in correlation to the true measures of TDF-DP. We will determine final dosing and measures following reporting from ongoing PK studies of pregnant women on PrEP (e.g. Impaact 2009).
- Two self-collected vaginal swabs will be taken at enrollment and at 1-month visit. These will be stored at -80°C at University of Cape Town until processing for STI testing (at 2-3 weeks) and end of study

for bacterial and viral metagenomic sequencing. Briefly this will include microbial DNA extraction and shotgun metagenomic sequencing as performed previously by the [name] Lab (Brown, BP Biorxiv 2019).

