## **3. Study design**

To address these objectives, we will conduct an observational cohort study in 1200 pregnant women who will be recruited at the first antenatal care (ANC) visit from the Gugulethu and one additional facility in the Hanover Park subdistrict of the Metro Region (to be identified in conjunction with provincial and local health authorities) Midwife Obstetric Units in Cape Town (n=600 pregnant women per site). We will follow the enrolled women through 12-months post-delivery.

**Setting.** The study will take place in two urban townships in Cape Town (Gugulethu and Hanover Park) with high HIV incidence that span the different socioeconomic, cultural, and ethnic groups in South Africa.

- Site 1: Gugulethu Midwife Obstetrics Unit (MOU)**
- Site 2: Hanover Park**

We selected those communities because of the high HIV prevalence there in pregnant and breastfeeding women, and because of the high number of mothers visiting every month for ANC and labour/delivery. Further, our team has several years' experience implementing research studies in those MOUs which will facilitate the integration of the study there. In 2017, Gugulethu saw over 3300 new ANC consultations per month, and 72%

(n=2300) are HIV-negative. Hanover Park has saw over 4900 new ANC consultations/month of which 87% are HIV-negative (n=4200). Considering our experience and patient flow, we are confident that at least 60 women/month per facility can be enrolled. Further, Drs. [name], [name] and colleagues have conducted research in the Gugulethu and Hanover Park communities for more than a decade and have substantial experience partnering with local health services. Building on this platform, we will use existing infrastructure in each clinic, including capacitating existing clinical providers, pharmacists and counselors, to provide PrEP care to pregnant and breastfeeding mothers. We will hire study staff to assist in the coordination, data management, and overall quality assurance of the counseling, drug provision and participation follow-up.

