##### Inclusion Criteria:

- 1.  $\geq 16$  years old**
- 2. confirmed HIV-negative (confirmed with a 4th generation antigen HIV test)**,
- 3. Intend on giving birth in the MOU facility**
- 4. confirmed to be pregnant**
- 5. without psychiatric or medical contraindications to PrEP.**

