## Adverse events:

- **Maternal adverse events:** We will collect data on maternal adverse events by asking mothers about intercurrent medical events, which will be reviewed by an obstetrician, including any hospitalizations or illnesses. We will also track and report changes in creatinine or other toxicities in women on PrEP.
- **Infant adverse events:** We will collect data on infant adverse events by asking mothers about infant health or intercurrent medical events, which will be reviewed by a pediatrician.
  - Adverse birth outcomes will include infants that were small for gestational age, pre-term births, miscarriage and stillbirths.

Table 1: PrEP-PP cohort measures by participant study month

and breastfeeding in local languages (at each visit)																
Routine ANC and postnatal care, well-baby visit follow-up (as available in standard of care), including rapid HIV testing, pregnancy, and birth outcomes	X	X	X	X	X	X	X		X		X		X			X
Survey to collect: behavioral acceptability, knowledge, and substance use data	X	X	X	X	X	X	X		X		X		X			X
Screening at enrolment for Hepatitis B and creatinine. If HBsAg+ = excluded from study; if creatinine eGFR<60, excluded from study	X															
Laboratory testing for STIs (chlamydia, gonorrhoea) & treatment if positive	X				X		X									
For women on PrEP:																
Laboratory tests of creatinine (if eGFR<60ml/min cannot continue on PrEP)	X			X												X
PrEP pharmacy refills and adherence supportive counseling monthly (for first 3 months on PrEP) then every 2 months for following months	X	X	X		X		X		X		X		X			X
Laboratory testing: renal function, hepatitis B; DBS taken for TDF-DP adherence measures (bi-monthly in participants on PrEP)	X	X	X		X		X		X		X		X			X
In-depth interviews for 30 participants per site (N=60) among 30 PrEP users and 30 non-PrEP users						X										X
Collect study data on: (1) PrEP counseling, (2) PrEP medication when requested, (3) regular appointments, (4) IEC materials, (5) adherence counselling and support by facility, through patient survey at every study visit	X	X	X	X	X	X	X	X	X	X	X	X	X	X	X	X
Vaginal swab for microbiome	X		X*													

\*between 24 and 28 weeks gestational age.

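### For women who start PrEP in pregnancy, baseline-to-end creatinine change spans delivery, and the planned user/non-user comparison cannot separate a PrEP effect from the end of pregnancy

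*Combined protocol and SAP*

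**What the plan says.** **Who is enrolled and for how long.** Protocol section 3 describes "1200 pregnant women who will be recruited at the first antenatal care (ANC) visit", followed to 12 months after delivery. The inclusion criteria require each woman to be "confirmed to be pregnant". Section 4 gives a mean follow-up of 18 months.

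**When creatinine is drawn.** The laboratory section heads the item "Renal function (in all women on PrEP" and states "Blood draws for creatinine levels will be taken at baseline, 3-month follow-up and at the end of the study". Step 9 of the enrolment visit ties the first draw to PrEP uptake: "For all participants who decide to take PrEP, the study nurse will draw blood to test for baseline creatinine tests". Follow-up Step 4 also confines the creatinine draw to participants on PrEP.

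**Where the schedule disagrees with itself.** In protocol Table 1 (measures by study month), the creatinine row for women on PrEP has three marks, which agrees with the laboratory section. Another row of the same table reads "Laboratory testing: renal function, hepatitis B; DBS taken for TDF-DP adherence measures (bi-monthly in participants on PrEP" and is marked at nine time points. A third row, "Screening at enrolment for Hepatitis B and creatinine", is not limited to women choosing PrEP, unlike Step 9.

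**How the result is used.** The protocol's adverse-events section groups creatinine changes with other toxicities in women on PrEP. SAP Table 1 (study measures for Aim 1) lists the outcome as "Any side-effects, change in creatinine clearance, any negative maternal or neonatal outcomes (for mother and infant) compared by PrEP use/non-use". SAP section 2.6, whose stated purpose is to describe harms of the intervention, counts creatinine-clearance changes among side effects. No section says which two samples make up a change, or splits creatinine by pregnancy state.

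**The concern.** A change score measures a drug effect only if nothing else that affects the measurement changes systematically between the two samples, or if a comparison group shares that other change. Neither condition holds here for women who start PrEP in pregnancy. Between their first and last samples they accumulate PrEP exposure and also stop being pregnant. The comparison group that could cancel the second change has no scheduled follow-up samples.

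Renal safety of the drug in pregnant and breastfeeding women is one of the results that readers will take from this cohort. The protocol's background describes the effect of TDF on filtration as small, and as reversible in PrEP trials. A contrast that also contains a pregnancy-related shift is poorly suited to detecting or excluding an effect of that kind, and could be reported as a fall in renal function on PrEP when there is none.

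**Working it through.** **1. The plan's own counts.** No figure is stated for creatinine change, but the cascade counts in SAP section 2.2 indicate how many women might have follow-up samples:
- initiators: 1200 × 0.60 = 720
- continuing at 12 months: 720 × 0.75 = 540
- adherent: 540 × 0.70 = 378

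All three match the SAP.

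**2. Where the samples fall.** Mean follow-up of 18 months less 12 months postpartum leaves 18 − 12 = 6 antenatal months on average. For an average woman starting PrEP at enrolment:
- baseline: about 6 months before delivery
- 3-month sample: about 6 − 3 = 3 months before delivery
- end of study: 12 months after delivery

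So only the last sample is non-pregnant. Taking delivery at 40 weeks and 3 months as 13 weeks (both assumed), the 3-month sample moves past delivery for a woman enrolled after 40 − 13 = 27 weeks. Enrolment at 24 weeks puts it at 37 weeks, still pregnant; enrolment at 28 weeks puts it at 41 weeks, postpartum. The visit text adds doubt: section 5 opens with visits every 3 months, while the follow-up section gives 1 month after baseline, then two months after birth.

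**3. Can the planned comparison remove the shift?** It would need non-users sampled at the same times. Step 9, follow-up Step 4, the laboratory section and the follow-up creatinine rows of protocol Table 1 all confine these draws to women on PrEP. At most, non-users have the enrolment screening value, if that row governs. They have no scheduled second value from which to form a change.

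**4. Possible size with no drug effect.** The documents give neither the direction nor the size of a pregnancy effect on filtration. *Assumption:* filtration in pregnancy is higher than the woman's non-pregnant level by a fraction x. Then

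apparent fall = 1 − 1/(1 + x)

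| Assumed rise x | Apparent fall | mL/min, if non-pregnant level is 100 (assumed) |
|---|---|---|
| 10% | 9.1% | 110 to 100 |
| 20% | 16.7% | 120 to 100 |
| 30% | 23.1% | 130 to 100 |
| 40% | 28.6% | 140 to 100 |
| 50% | 33.3% | 150 to 100 |

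**5. Would sampling error mask it?** The 95% half-width for a mean change is 1.96 × SD/√n. With n = 540 and an assumed SD of within-woman change of 15 to 35 mL/min:
- SD 15: 1.96 × 15/√540 = 1.3 mL/min
- SD 35: 1.96 × 35/√540 = 3.0 mL/min

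Even the smallest case, a 10 mL/min fall with SD 35, gives z = 10/(35/√540) = 6.6. The number of women with both samples may be below 540, since that count refers to 12 months. With n = 378 the same case gives z = 10/(35/√378) = 5.6. More women would make the estimate more precise without making it less biased.

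**The case against.** The strongest reply is that the plan never fixes change as end of study minus baseline. SAP section 2.6 describes frequencies of side effects by counts and person-time, plus highest grade, which is event counting and not a mean change. The only numeric renal criterion is an eGFR of 60, and a woman going from 120–150 to 100 mL/min never approaches it. This stands. A reader might infer that the SAP commits to a baseline-to-end contrast and that the return from pregnancy will be reported as renal decline. The documents support neither step: the outcome is descriptive, and no renal-decline endpoint is defined. What they support is that the contrast is left open and the obvious choice is confounded.

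It is also tempting to say that the problem affects every woman. It does not. The protocol offers PrEP at later visits, including postpartum ones, and a woman whose baseline is a postpartum draw at PrEP start is not affected. Women censored before delivery have no cross-delivery pair.

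If the bi-monthly renal row of protocol Table 1 governs, many pairs within pregnancy or within the postpartum period would exist. That is fair. It makes a clean analysis easier, but the laboratory section says otherwise and the SAP does not say how such samples would be used.

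The named user/non-user comparison would be the natural control if non-users were sampled at the same times; they are not scheduled to be. The general pregnant/postpartum subgroup in SAP section 2.7 shows that pregnancy state is on the authors' minds, but it cannot repair a change score whose two ends lie on either side of delivery.

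**Conclusion.** The concern holds for women who start PrEP in pregnancy and complete follow-up. In their baseline-to-end creatinine change, PrEP exposure and the pregnancy-to-postpartum transition cannot be told apart, and the comparison named in SAP Table 1 has no scheduled non-user follow-up samples with which to separate them. That part follows from the schedule alone.

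The size rests on assumptions from outside the documents: a 10% to 50% rise in filtration in pregnancy gives an apparent fall of 9% to 33% with no drug effect. This affects a descriptive secondary safety outcome and leaves the cascade results untouched. It should be corrected, because the undefined change invites a misleading safety statement and the correction is mainly SAP wording.

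**What to change.** In SAP Table 1 and section 2.6:

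- Define change as measured from the draw at PrEP start, and name the later sample used.
- Report creatinine and eGFR levels, and the proportion below the protocol's existing eGFR threshold, at each draw by pregnant or postpartum state, with gestational age for antenatal draws.
- Report change separately for pairs drawn in the same state and for pairs that cross delivery. State that cross-delivery change is descriptive and is not attributed to PrEP. Keep these data: on the three-draw schedule they are most of the long-term renal information for women who start in pregnancy.
- Drop the user/non-user comparison of creatinine change, since non-users have no scheduled follow-up samples.

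In the protocol, reconcile the laboratory section with Table 1 (three draws against the bi-monthly renal row), and Step 9 with the Table 1 enrolment-screening row on who has the first draw.

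**Cost.** SAP wording and one protocol reconciliation, with no new samples. Gestational age at baseline and at delivery is already to be described, so state at each draw can be derived. The downside is that fewer women contribute to the same-state change score, and on the three-draw schedule few of those who start in pregnancy would have a same-state pair beyond 3 months.
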